**1. Develop interview guides informed by PRISM domains and implementation prototypes (Table 1).**

Using PRISM domains, interview guides will be developed with iterative feedback from the CAB. I will examine topics including those affecting implementation of the program and participation in LIVESTRONG and

implementation strategy prototype screenshots for feedback.

- I will create screenshot prototypes of implementation strategies to be adapted, including the referral webform (Figure 5) and a patient progress report (Figure 7).

Figure 7. Sample patient progress report used by a successful LIVESTRONG Program.

Dear [Health Care Provider Name],							
Your patient, [First Last] (DOB [x/x/xx]), participated in LIVESTRONG at the YMCA, available to your patients through the YMCA. [Name] attended [X] of 24 class sessions. Below, you will find the pre and post-assessment data for the patient named above.							
6 minute walk test		Strength Testing		Back Scratch		Arm Reach	
Total Dist. (m)	Leg Press (lbs)	Chest Press (lbs)	Right Up (cm)	Left Up (cm)	Total Reach (cm)	Right (seconds)	Left (seconds)
Pre 450	140	45	-6.5	-3.5	40	8	9
Post 512	150	45	-5	3.5	45	10	30

**Program Details**

- 12-week program with two 90-minute sessions per week
- Includes cardiovascular conditioning, strength training, balance, and flexibility exercises
- Evaluation includes fitness and quality of life assessments before and after participation
- Facilitated by YMCA-certified instructors
- Free YMCA membership for participant and their family for the duration of the program

Please continue to support your patients by referring them to LIVESTRONG at the YMCA available through the [YMCA name]. We look forward to sharing your patient's progress with you. Do not hesitate to contact me if you have any other questions.

Table 1. Examples of interview questions mapped on to PRISM domains.

PRISM Domain	Example of Key Questions Relevant to ActivityLink
Program (Intervention) Organizational perspective Patient perspective	
 
What steps are needed to prepare key staff to identify and screen patients? To conduct the program? How can the system best be embedded into workflow?
 
How can the program be more patient-centered and less complex for patients? Does it address important patient barriers to response?
 

External Environment	
 
Are there community/outside resources that can enhance intervention?
 

Implementation & Sustainability Infrastructure	
 
How can existing infrastructure be used to handle key implementation/sustainability tasks?
 
Can implementation/sustainability tasks be part of key staff/Navigator job descriptions?
 

Recipients Organizational characteristics Patient characteristics	
 
Which available systems can best support implementing the program? Do key staff expect the program to be sustainable?
 
What are common knowledge, beliefs and perceived risk patterns among patient recipients? (modifiable factors regarding patient perceived net benefit)
 

- Obtain feedback from key stakeholders.** I will conduct semi-structured phone interviews (30-minutes) with UMMHC breast patient navigators (n=2), oncologists/radiologists (n=2), cardiologists (n=2), and patients (n=2) who are not part of the CAB. I will ask clinical stakeholders about current workflow for physical activity counseling/referrals or anticipated changes in workflow that need to be made using use-cases, often used by software engineers, to elicit workflow depiction. Use cases describe how a user completed a task in a sequence of simple steps, beginning with a user's goal and ending when that goal is fulfilled. Thus, it is easier for the user to understand the workflow and highlight issues/provide additional details about the use-case. Under [name] guidance (a software engineer), I will use my clinical shadowing experience and field notes (see Training Plan) to develop initial use-cases as prompts for the discussion. **Recruitment:** I will use established partnerships and snowball sampling to recruit clinic staff and physicians and information extracted from EHR to identify patients for recruitment (HIPAA waiver). Navigators will aid in this effort.

**Sub-Aim 1a Data Analysis:** Under the direction of the qualitative advisor, [name], I will transcribe interviews verbatim and use a coding start-list based on protocol content (deductive) followed by open coding driven by immersion in the data (inductive). Myself and one other research team member with experience analyzing qualitative data will each code >10% of transcripts and coding checks will be completed to ensure inter-rater reliability. Disputes in coding decisions will be discussed within the research and mentor team until resolved and a kappa > 0.75 is attained, at which point the entire dataset will be coded. Based on the use-cases, I will also create a workflow map using swimlanes (Lucid software) to document what the actual workflow of the patient navigator is surrounding physical activity counseling/referrals. This will include their communication and interactions with oncologists, cardiologists and other clinic staff. I will then present these results to the CAB to refine the program as discussed in Aim 1c.

**Sub-Aim 1b (Months 6-8): Refine the e-referral Web form using think aloud usability testing with Navigators.** I will perform usability testing with our users, present feedback to the research team and the CAB and make iterative refinements to the protocol as needed.

- Conduct usability testing.** I will use "Think Aloud" protocols as follows: While users are reviewing the content, they will be asked to vocalize thoughts, feelings, and opinions while interacting with the system. Think Aloud allows you to understand how the user approaches the interface and what considerations they keep in mind while using. Participants will complete a rating instrument including questions addressing the

acceptability, accuracy, ease of use and satisfaction with the system. Since the recommendation indicates that the majority of issues can be identified with 4±1 users, I will test the system with up-to 5 navigators.

a. **Analysis:** Testing sessions will be transcribed, data segmented and codes applied to identify themes in the data. I will combine these themes with field notes to design usability reports.

2. **Systematically compare users' feedback.** To determine the need for refinements and additional testing, we will present reports to the CAB. If 50% or more of participants have difficulty achieving a task within the system, I will consider this problematic and revise that feature with iterative feedback from users'. I will use this iterative process until less than 50% of participants are having issues with completing the tasks.

**Sub-Aim 1c (Months 8-12):** Refine the e-referral additional components to support integration into the clinical workflow (paper prescription form, reminders, training and booster program and feedback) for navigators using feedback from aims 1a and 1b. I will work iteratively with the CAB. Specifically, I will:

1. Create feedback summary reports based on aims 1a and 1b.
  - a. Barriers and facilitators, implementation strategies, clinical workflow and usability reports.
2. Create new clinical workflow swimlane mapping and protocol including strategies and e-referral.
3. Meet with the CAB, present feedback reports, swimlane mapping and protocol.
4. Based on feedback, refine clinical workflow and protocol. Re-distribute to CAB for approval.
5. Develop final version of protocol and swimlane workflow mapping to be beta tested in Aim 2.

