**Recruitment, Screening, Informed Consent and Data Collection:** The Breast clinic employs 10 patient navigators. **Inclusion Criteria:** Navigators in the UMMHC Breast Clinic will be eligible to participate if they: 1) are employed as a navigator of the clinic and 2) provide written informed consent. **Navigator Recruitment:** I have already developed relationships with clinic navigators and will provide information on the study enrollment at their monthly in-service meeting. Interested navigators will complete an informed consent prior to enrolling in the study. **Patient Recruitment:** I will use an opt-out strategy for recruiting patients for the follow-up interview. Based on the workflow designed, eligible patients will be screened and referred to the program by the navigator. For those who agree to be referred, the navigator will enter their information to the e-referral system. For these patients and those who do not want to be referred, navigators will also document their contact information and reasons for not joining the program/refusing referrals as part of their clinical workflow. Navigators will also provide a brochure that will include information about the research study and that someone may contact them for a follow-up interview. The brochure will include contact information (email, text, and mailing information) for them to use to opt out of the follow-up interview if they wish to do so. I, or my research staff will then contact patients who have not opted out to schedule an interview. **Data Collection:** Follow-up phone calls with navigators, a sub-sample of patients and LIVESTRONG staff will be done to conduct qualitative assessments (verbal informed consent prior to the interview). I will also collect quantitative measures to assess number of referrals.

**PDSA Cycle 1: Plan** - Using feedback from Aim 1, ActivityLink wave 1 will go live 8 weeks prior to the start of the 3rd quarterly LIVESTRONG session (October 2021). I will use the plan designed and informed by the CAB in Aim1c for the program implementation. Navigators will undergo training on implementing ActivityLink and receive detailed protocol and workflow mapping prior to the start.

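### Does the 50% revision rule in the usability test leave difficulties met by only one or two of five navigators unaddressed?

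*Combined protocol and SAP*

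**What the plan says.** Section 3.3h, Sub-Aim 1b, tests the Web form with at most 5 navigators. The number rests on a cited recommendation that "the majority of issues can be identified with 4±1 users". The item on comparing users' feedback gives the only numeric rule: "If 50% or more of participants have difficulty achieving a task within the system, I will consider this problematic and revise that feature". It also sets the end point: "I will use this iterative process until less than 50% of participants are having issues with completing the tasks".

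The same item opens with a route that carries no threshold: "To determine the need for refinements and additional testing, we will present reports to the CAB". Those reports are built from all coded themes plus field notes. The opening of Sub-Aim 1b adds that the investigator will "make iterative refinements to the protocol as needed". Section 3.3c puts usability and refinement within the CAB's remit and lists patient navigators among its members. Sub-Aim 1c then takes the usability reports back to the CAB, although its stated purpose is different: "Refine the e-referral additional components to support integration into the clinical workflow". On the size of the user group, section 3.3i says: "The Breast clinic employs 10 patient navigators".

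**The concern.** The sample size and the action rule appear to rest on different probabilities. A handful of users is enough to identify an issue if identifying means seeing it at least once. The compulsory rule needs half of the testers to struggle: 2 of 3, 2 of 4 or 3 of 5. A difficulty met by 2 of 5 navigators would thus be observed, would compel nothing, and would satisfy the stopping rule. Rounding adds an oddity: the rule is harder to reach with 5 testers than with 4.

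Navigators enter referrals through this form, and the beta test takes its referral counts from the same system. If a known difficulty stayed in place, it could depress wave 1 referrals and be mistaken for reluctance among navigators or patients.

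**Working it through.** **Inputs from the plan.** Testers: n up to 5, with 3 to 5 as the cited range. Rule: at least half of n, so r = 2, 2, 3 for n = 3, 4, 5. Clinic pool: 10 navigators. The plan gives no per-user probability of difficulty, p, so the sample size cannot be re-derived; 5 is simply the top of the cited range. A range of p is assumed below.

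**Is the sizing statement plausible?** Taking identified as seen at least once, the probability is 1 − (1 − p)^n. It exceeds one half when p > 1 − 0.5^(1/n), that is p > 0.206, 0.159 or 0.129 for n = 3, 4, 5. The statement is reasonable unless difficulties are rare.

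**Seen versus rule met.** P(seen) = 1 − (1 − p)^n. P(rule met) = Σ C(n,x) p^x (1 − p)^(n−x), summed over x from r to n.

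| p (assumed) | Seen, n = 5 | Rule met, n = 5 | Rule met, n = 4 | Rule met, n = 3 |
|---|---|---|---|---|
| 0.2 | 0.672 | 0.058 | 0.181 | 0.104 |
| 0.3 | 0.832 | 0.163 | 0.348 | 0.216 |
| 0.4 | 0.922 | 0.317 | 0.525 | 0.352 |
| 0.5 | 0.969 | 0.500 | 0.688 | 0.500 |

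Worked case, n = 5 and p = 0.3: seen = 1 − 0.7^5 = 0.832; rule met = 10(0.027)(0.49) + 5(0.0081)(0.7) + 0.00243 = 0.163. The difference, 0.669, is 80% of the occasions on which the difficulty is seen.

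**Finite pool.** Suppose 5 of the 10 navigators are drawn at random (the plan does not say they are) and K of the 10 would have difficulty. There are C(10,5) = 252 possible draws.

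- K = 2: seen 1 − 56/252 = 0.778; rule met 0.
- K = 3: seen 1 − 21/252 = 0.917; rule met 21/252 = 0.083.
- K = 4: seen 1 − 6/252 = 0.976; rule met (60 + 6)/252 = 0.262.
- K = 5: seen 1 − 1/252 = 0.996; rule met 126/252 = 0.500.

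**What the figures measure.** Rule met means revision is compulsory. The harm would be a difficulty left in the form after the CAB had seen the report, and neither the plan nor these figures give that probability. The figures also depend on how the stopping rule is read. It speaks of tasks in the plural, so it can mean that fewer than half of participants have an issue on any task. With five tasks and an independent p = 0.2 on each (both assumed), a user has at least one issue with probability 1 − 0.8^5 = 0.672. Then 3 or more of 5 users have one with probability 0.80, against 0.058 for a single task.

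**What happens below the rule.** The reports are not restricted to tasks at or above 50%, so a difficulty in 1 or 2 of 5 can reach the CAB. The CAB's task at that point is to decide on refinements and further testing. Sub-Aim 1c presents the feedback reports again, drafts a workflow and protocol that include the e-referral, and returns the refined version to the CAB for approval. In Aim 2 (section 3.3i) navigators are trained before going live, receive weekly calls and emails over 8 weeks, and at least one navigator interview takes place every 2 weeks. The CAB then helps decide adaptations before wave 2.

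**The case for a change.** The best case for a change is that neither the CAB route nor the as-needed refinement states a count, a severity grade or a record of the decision. A difficulty seen in 2 of 5 could be reported, meet the stopping rule and remain, with nothing written about why. Sub-Aim 1c is chiefly about the supporting components, and the as-needed sentence refers to the protocol rather than to the form. Each wave lasts only 8 weeks, so repairing known faults beforehand is more efficient, and a short log would cost little.

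The factual part stands: the discretionary route has no written criterion, and a 2-of-5 difficulty passes the numeric rule. It does not follow that such difficulties go unhandled. A board that includes navigators and is asked what needs refining would be expected to weigh them. Revising whatever any single tester finds hard is a different design preference, which risks editing the form for idiosyncratic problems. Both the 4±1 figure and the 50% rule are attributed to usability references, and experienced teams differ on where to set such a trigger. The unevenness between 4 and 5 testers is a rounding effect of any half-of-users rule at these numbers.

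**Conclusion.** No change is needed. Observing broadly, compelling revision of common difficulties and leaving the rest to an informed board is a coherent and fair trade-off for formative testing with at most 5 users. What is missing is operational detail that the team can fill sensibly, for instance by noting in the planned usability reports which difficulties fell below half and what the CAB decided.

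The gap between seeing a difficulty and being compelled to act on it is real: 0.832 against 0.163 at p = 0.3 with 5 testers. It rests on assumed values of p, on one reading of the stopping rule and on independence between users, and it does not estimate difficulties left unrevised. No stated number in the plan is wrong because of it. Aim 2 reports referral counts descriptively only, and the refinement between waves gives a further chance to correct the form. The conclusion assumes that the CAB receives the full usability reports, as the plan describes.

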**3.3i. Specific Aim 2 (Months 12-22): Beta test in UMMHC Breast Clinic and refine based on user feedback.**

This Aim will provide insight into feasibility and acceptability of ActivityLink delivered by navigators to survivors at risk of CVD. I will beta test the program in 1 clinic and at 3 YMCAs (3.3d. Setting). Beta testing is commonly conducted in iterative cycles and used to verify program readiness and user satisfaction prior to a full-scale launch. Results from beta testing will inform a larger, multi-site feasibility pilot trial resulting in randomization at the level of the clinic mirroring my mentors' prior work.

[figure not shown]
**Design:** I will beta test ActivityLink in two waves using Plan, Do, Study, Act (PDSA) Cycles. PDSA cycles are best used to test ideas on a small scale prior to full implementation and are commonly used for implementation of projects into clinical workflow. As detailed below, the initial wave will be 8-weeks in length and used to refine ActivityLink for the second wave (8 weeks). Waves will be timed with the LIVESTRONG program calendar (new sessions begin in January, April, July and October). Thus, I plan to conduct the first wave for the October 2021 session and the second wave for the January 2022 (Figure 8).

**Recruitment, Screening, Informed Consent and Data Collection:** The Breast clinic employs 10 patient navigators. **Inclusion Criteria:** Navigators in the UMMHC Breast Clinic will be eligible to participate if they: 1) are employed as a navigator of the clinic and 2) provide written informed consent. **Navigator Recruitment:** I have already developed relationships with clinic navigators and will provide information on the study enrollment at their monthly in-service meeting. Interested navigators will complete an informed consent prior to enrolling in the study. **Patient Recruitment:** I will use an opt-out strategy for recruiting patients for the follow-up interview. Based on the workflow designed, eligible patients will be screened and referred to the program by the navigator. For those who agree to be referred, the navigator will enter their information to the e-referral system. For these patients and those who do not want to be referred, navigators will also document their contact information and reasons for not joining the program/refusing referrals as part of their clinical workflow. Navigators will also provide a brochure that will include information about the research study and that someone may contact them for a follow-up interview. The brochure will include contact information (email, text, and mailing information) for them to use to opt out of the follow-up interview if they wish to do so. I, or my research staff will then contact patients who have not opted out to schedule an interview. **Data Collection:** Follow-up phone calls with navigators, a sub-sample of patients and LIVESTRONG staff will be done to conduct qualitative assessments (verbal informed consent prior to the interview). I will also collect quantitative measures to assess number of referrals.

**PDSA Cycle 1: Plan** - Using feedback from Aim 1, ActivityLink wave 1 will go live 8 weeks prior to the start of the 3rd quarterly LIVESTRONG session (October 2021). I will use the plan designed and informed by the CAB in Aim1c for the program implementation. Navigators will undergo training on implementing ActivityLink and receive detailed protocol and workflow mapping prior to the start.

**Do** - During the implementation of ActivityLink navigators will receive booster phone calls and emails weekly (8 each) to encourage implementation and troubleshoot any issues. **Measures:** Throughout the implementation period, I will interview navigators using ActivityLink, patients who have been referred (accepted and declined) and LIVESTRONG site Program Directors. Navigator interviews will examine RE-AIM measures

Figure 8. PDSA Cycle (2 cycles).

(see Table 2) associated with the ActivityLink and any additional questions identified from the CAB. I will conduct at least 1 navigator interview every 2 weeks. Patient and LIVESTRONG staff interviews will examine barriers, facilitators and preferences of the ActivityLink referral process. I will interview patients (n=2-3) who were referred to the program (identified by our e-referral system), patients who declined (n=2-3) and LIVESTRONG Program Directors (n=3) starting 2 weeks after each wave launches. I will collect data navigators recorded from patients who refused the referral. Number of referred patients (from e-referral system) and number refused (from navigator documentation) will be collected during the 8 weeks.

**Study** - For qualitative analysis, I will use a similar protocol to Aim 1a (deductive followed by inductive approach. Transcripts will be coded by myself and 1 other research team member using coding checks (10% transcripts) to ensure inter-rater reliability. We will resolve disputes in coding (> 0.75 Kappa) and then the entire dataset will be coded. Quantitative data will not be analyzed due to the small sample size, though I will present descriptive statistics of number of referrals, number of declined referrals and proportion of eligible patients referred (based on number of survivors treated in the clinic during the wave) and present to the CAB.

**Act** – I will organize results and present them to the CAB to help determine the need for adaptations to the system. Using the CABs feedback, we will develop action-items for changes to be made in Cycle 2.

**PDSA Cycle 2:** The CAB will help to determine adaptations needed to the new implementation plan. The second ActivityLink wave will go live 8 weeks prior to the January 2022 session and navigators will be trained on the newly adapted system. I will collect the same qualitative and quantitative measures as identified in PDSA Cycle 1. At the conclusion of wave 2 (Act), I will work with the CAB to refine and package ActivityLink to be ready for testing in pilot feasibility trial (see section 3.4).

Table 2. Qualitative sample navigator interview questions mapped on to RE-AIM measures.

RE-AIM Measures	Sample Questions
Reach	
 
• What factors contribute to the participation/non-participation of the participants?
 
• What might have been done to get more of the target audience to participate?
 

Adoption	
 
• What factors contributed to the organization and its individuals taking up ActivityLink?
 
• What barriers interacted with the ActivityLink to prevent adoption?
 
• Was there partial or complete adoption?
 
• Why did some staff members in these organizations participate and others did not?
 

Implementation	
 
• How was the ActivityLink implemented? By whom and when?
 
• What influenced implementation or lack of implementation?
 
• What combination of implementation effects affected the outcome results?
 
• How and why was the program adapted or modified over time?
 

Maintenance	
 
• Do you foresee ActivityLink being implemented after the program core period?
 
• What is needed to maintain this program?
 

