**3.1c. Physical Activity reduces CVD Risk.** Over 75% of deaths due to CVD could be prevented with adequate lifestyle changes. Decades of research show physical activity has a cardioprotective effect on lowering CVD risk. In addition to treating risk factors, physical activity also mediates cardiotoxic effects of cancer treatments and is associated with improved health outcomes after breast cancer diagnosis.

**3.1d. Though safe and effective, few survivors are physically active.** Physical activity has been deemed safe and efficacious for survivors by the American College of Sports Medicine and supported by the American Cancer Society. Though the direct effect of exercise on CVD prevention in patients with breast cancer has yet to be evaluated in long-term randomized trials, achieving physical activity guidelines is highly recommended. Due to the increased number of survivors, researchers have placed an emphasis on lifestyle interventions, including physical activity promotion to improve quality of life and counter disease progression and other comorbidities. However, less than 10% of patients will be physically active during treatment and only 20-30% physically active after treatment. Survivor-reported barriers include program accessibility, affordability and parking, while facilitators included convenient and survivor friendly environments.

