**In conclusion,** my preliminary data demonstrates: 1) Survivors face clinic barriers to physical activity guidance and referrals, 2) LIVESTRONG programs that are successful in recruiting have referral and feedback methods established with providers, and 3) My ability to establish relationships and work with clinic, community and patient stakeholders, making this project feasible.

**3.3b. Study Overview:** I will develop ActivityLink, an adapted e-referral implementation program to increase participation in an evidence-based physical activity program (LIVESTRONG at the Y). ActivityLink will be adapted to a new setting and population from a previously used e-referral implementation program (Aim 1) and then beta tested (Aim 2) to set the stage for a future large feasibility pilot trial (Figure 2). In Aim 1, I will conduct formative work (1a), usability testing with navigators (1b) and refinement of ActivityLink to be integrated into clinical workflow (1c). Lastly, I will use 2 process cycles to beta test and refine ActivityLink for navigators to deliver to survivors with a CVD risk factor of physical inactivity (Aim 2). My formative work with clinical partners supports the navigator's delivery of the ActivityLink.

**3.3c. The Clinic and Community Advisory Board (CAB):** First I will finalize the partially established CAB. The CAB will bring together constituents from the clinic and community to provide feedback on the overall project,

including interview questions, workflow mapping, usability and refinement of the implementation program and adaptations during beta testing. The CAB will meet bi-monthly in year 1. In year 2, we will frontload the 6 meetings to match to the timing of our PDSA cycles. The CAB will consist of key stakeholders with whom I have already established relationships: UMMHC patient navigators, cardiology and oncology providers, YMCA-USA, LIVESTRONG staff and participants. I will include 1 member of the UMMS Center for Clinical and Translational Science, Science Participation Recourse Center's Community Advisory Board will (increase engagement of special populations in translational research through tailored, culturally responsive strategies).

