**3.3d. Setting:** I will conduct the study in the Breast Clinic at UMMHC University Campus. The clinic is situated in Worcester, MA, with a population of 57.1% White, 20.9% Hispanic or Latino, and 11.8% Black or African American. The median household income is \$45,869; 35.8% of the people speak a non-English language. The clinic employs 10 patient navigators who we will work with throughout the entirety of the study. In 2016 the clinic treated 461 women, with ~40% (n=184) of women living <9 miles from the Clinic (Figure 3). Breast Clinic data from 2016 showed that ~89% of the patients were White, though data on ethnicity and socioeconomic status are lacking. I will work with three

YMCA branches within a 6-mile radius of the clinic: 1) Boroughs Family Branch YMCA (Westborough, MA), 2) Central Community Branch YMCA (Worcester, MA), and 3) Greendale YMCA (Worcester, MA). Though the Breast Clinic and YMCA sites have lower proportions of minority and underserved survivors, I chose them for convenience for this K12. I plan to work with more diverse sites in future.

[figure not shown]
**3.3e. LIVESTRONG at the Y – an evidence-based community-based physical activity program designed for survivors:** The evidence-based intervention to which navigators will refer patients is LIVESTRONG at the Y. As previously stated, LIVESTRONG is an evidence-based 12-week physical activity program free of cost to survivors. The program has shown increases in physical activity levels, aerobic fitness and physical function. Survivors are able to participate at any point following a cancer diagnoses with physicians' clearance. Enrolled participants will attend 2 sessions/week for 12 weeks. Sessions focus on aerobic, strength, balance and flexibility exercises and participants are tested at baseline and again at the end of the 12-week program. LIVESTRONG is offered in over 800 communities across the U.S.

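### The planned referral proportion divides navigator-entered referrals by every survivor treated, so it mixes navigator uptake with patient referral and is not a proportion of eligible patients

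*Combined protocol and SAP*

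**What the plan says.** Section 3.3i (Specific Aim 2) tests ActivityLink in two 8-week waves. On navigators, its recruitment paragraph says "The Breast clinic employs 10 patient navigators" and "Interested navigators will complete an informed consent prior to enrolling in the study". It sets no target or minimum number. Section 3.3d is more expansive: "The clinic employs 10 patient navigators who we will work with throughout the entirety of the study".

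On referrals, section 3.3i says "For those who agree to be referred, the navigator will enter their information to the e-referral system". The Do step adds: "Number of referred patients (from e-referral system) and number refused (from navigator documentation) will be collected during the 8 weeks".

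The Study step limits the quantitative data to three descriptive results for the advisory board (CAB): the count of referrals, the count of declined referrals, and the "proportion of eligible patients referred (based on number of survivors treated in the clinic during the wave". Cycle 2 repeats these measures. The plan lists no count of navigators enrolled or referring, and no count of patients screened, found eligible or offered referral.

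The inclusion criteria in section 3.3i cover navigators only. The target patient group comes from section 3.3b, where navigators are to "deliver to survivors with a CVD risk factor of physical inactivity".

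**The concern.** The numerator and denominator describe different groups. The numerator can include only women whom a navigator using the system saw, offered a referral and enrolled. The denominator also includes women whose navigator may not have joined, and women who are already active and so outside the target group. The label nevertheless says eligible patients.

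The figure goes to the CAB, which uses the wave 1 results to choose changes for Cycle 2. A low value could mean that few navigators joined, that those who joined did not offer referral, or that patients declined. Each calls for a different change. Failure to offer is a realistic possibility: section 3.3g reports that in beta testing of the predecessor system practices forgot to make referrals. A rise between waves is equally ambiguous, because higher navigator enrolment alone would raise the figure.

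**Working it through.** The plan gives no expected referral proportion or sample size, so there is no planned figure to reproduce. The check is direct arithmetic.

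**Inputs from the plan.** 10 navigators (3.3d, 3.3i); 461 women treated in 2016 (3.3d); 8-week waves (3.3i). On activity, section 3.1d says "less than 10% of patients will be physically active during treatment and only 20-30% physically active after treatment", which leaves roughly 70% to 90% inactive.

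**Assumptions, not in the plan.** 2016 volume is typical and evenly spread, so a wave has W = 461 × 8/52 = 70.9 survivors. Each survivor has one navigator. Caseloads are equal unless stated.

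**Formula.** Planned proportion = s × e × o × a, where
- s = share of treated survivors seen by participating navigators,
- e = share of those who are eligible,
- o = share of eligible women offered referral,
- a = share of offers accepted.

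The upper limit is s × e, reached when o = a = 1.

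**Upper limit when k of 10 navigators enrol.**
- Equal caseloads, all eligible (s = k/10, e = 1): 50% at k = 5, 80% at k = 8, 100% at k = 10.
- Unequal caseloads, with illustrative weights 1 to 10 (sum 55): at k = 5 from 15/55 = 27% to 40/55 = 73%; at k = 8 from 36/55 = 65% to 52/55 = 95%.
- Equal caseloads with 70% to 90% eligible: 35% to 45% at k = 5, and 70% to 90% even at k = 10.

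**Can the planned counts separate the causes?** Take equal caseloads and e = 1. Referred = W × s × o × a, and declined = W × s × o × (1 − a).

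| | Enrolled | Offered | Accepting | Referred | Declined | Planned proportion | Referred / seen by enrolled navigators |
|---|---|---|---|---|---|---|---|
| A | 5/10 | all | 60% | 21.3 | 14.2 | 30% | 60% |
| B | 10/10 | all | 30% | 21.3 | 49.6 | 30% | 30% |
| C | 10/10 | half | 60% | 21.3 | 14.2 | 30% | 30% |

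The proportion is 30% in all three. The declined count separates A from B (acceptance 60% against 30%). It does not separate A from C, where all three planned results agree. Reporting enrolment and the restricted proportion separates A from C. The number offered (35.5 of 35.5 in A, 70.9 of 70.9 in B, 35.5 of 70.9 in C) then separates B from C.

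**Change between waves.** If enrolment rises from 6 to 8 navigators and half of each navigator's patients are still referred, the figure moves from 0.6 × 0.5 = 30% to 0.8 × 0.5 = 40%, with no change in what happens to a patient whose navigator takes part.

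**The case against.** The case for leaving the plan alone has substance.

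- **The CAB does not see a single number.** It also receives the referral and declined counts and the coded interviews. A reader might infer that low uptake and poor patient acceptance cannot be told apart at all. The documents do not support that: if every patient is offered referral, the declined count tells them apart, as A and B show.
- **Adoption is explored in interviews.** Table 2 asks about partial adoption and why some staff did not take part. The team consents, trains and calls the navigators, so it will know how many enrolled; what is missing is a reporting line. This stands, but only in part. The interviews are with navigators using ActivityLink, at least one every two weeks (8/2 = 4 per wave at minimum), and navigators who never enrol are not a listed interview group.
- **Only consenting navigators refer: this is an inference.** A reader might take it as stated. Section 3.3i requires consent to take part but does not say that a non-consenting navigator cannot use the system, and section 3.3d anticipates working with the 10 navigators throughout. If all 10 enrol, the enrolment limit is gone.
- **A ceiling of k/10 is not a result of the plan.** It needs equal, non-overlapping caseloads and every survivor eligible, and the documents give none of these. If navigators share patients, the limit may not bind.
- **The figure is descriptive**, its denominator is disclosed in the same sentence, and no threshold rests on it.

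These points narrow the concern and lower its weight. They do not answer the A-against-C ambiguity, or the use of all treated survivors under an eligibility label.

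**Conclusion.** The point holds in a limited form and is minor. The reported proportion is bounded by the share of treated survivors who are eligible and seen by participating navigators. Even with the declined count beside it, it cannot separate navigators who did not enrol from enrolled navigators who did not offer referral.

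The size depends on enrolment and caseloads, which the plan does not give. With half the navigators enrolled and all survivors eligible, the limit is 50% under equal caseloads and 27% to 73% under the illustrative unequal ones. The eligibility mismatch is the firmer part: it needs no assumption about enrolment or caseload, and with 70% to 90% of survivors inactive it holds the figure to at most 70% to 90% even when all 10 navigators take part.

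The plan's own background keeps such quantities apart: section 3.3a.iv gives the share of practices using the predecessor system (93%) separately from the referral percentages (33% and 11%). Aim 2 lists no numerical counterpart for adoption.

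**What to change.** In the Study step, for both waves, report:

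- (a) navigators enrolled, and navigators making at least one referral, each out of 10;
- (b) survivors referred over eligible survivors (screened as physically inactive) seen by enrolled navigators, together with the number offered referral.

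Keep the clinic-wide figure, but label it as reach among all treated survivors instead of as a proportion of eligible patients.

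Item (a) costs almost nothing, since the team holds the consent records and the e-referral system should show who referred. Item (b) needs participating navigators to log patients screened and offered, or a clinic list that links each patient to a navigator. With the list alone, the denominator would be all survivors seen by enrolled navigators and should be labelled so. Where neither is possible, report (a) beside the relabelled clinic-wide figure. No change to design, sample or timeline is needed.
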